10.1 Visit 2 (Baseline): (Within 3 months of Visit 1)

Some procedures performed in this visit may be performed in Visit 1 provided that Informed Consent has been signed.

1. Urine pregnancy test for Women of Child Bearing Potential (WOCBP)

-
2. Quantitative MRI;
 3. Kinematic movement;
 4. Assessment of muscle strength, isokinetic dynamometry;
 5. Functional performance testing.

After randomization is performed, a Study Team member will then inform the Vail Hospital pharmacist of the subject's assigned randomization code, and obtain study medication. Subjects will take their first dose of study medication at the clinic.

Subjects will be instructed to self-medicate for day 2 followed by 28 days off. A second course will be taken for two consecutive days (days 31 and 32).

A Medication Log recording medication administration will be provided to the subject with instructions to complete during the period of administration.

10.2 Visit 3: Two Weeks after first dose of Fisetin or Placebo (+/- 2 days)

All subjects will return to the study site 2-weeks from the subject's last dose of Fisetin or placebo. The following procedures will be performed:

1. Blood Analysis.

10.3 Visit 4: Two Weeks from the Subject's Last Dose of Fisetin or Placebo (+/- 10 days)

All subjects will return to the study site two-weeks from the subject's last dose of Fisetin (FIS) or placebo. The following procedures will be performed:

1. Vital signs;
2. Medical and surgical history;
3. Physical exam with ROM of target limb;
4. Blood analysis;
5. Medications;

-
6. Completion of augmented PROs, including: NRS, IKDC, Lysholm, TEGNER, WOMAC and SF-12;
 7. Protocol deviation assessment;
 8. Adverse event assessment.

10.4 Visit 5: Six Months from the Subject's First Dose of Fisetin or Placebo (+/- 4 weeks)

1. Vital signs;
2. Medical and surgical history;
3. Physical exam with ROM of target limb(s);
4. Blood analysis;
5. Completion of augmented PROs, including: NRS, IKDC, Lysholm, TEGNER, WOMAC and SF-12;
6. Medications;
7. Protocol deviation assessment;
8. Adverse event assessment;
9. Quantitative MRI;
10. Lower-extremity kinematic testing with video-motion analysis;
11. Isokinetic dynamometry testing;
12. Functional performance testing.

10.5 Visit 6: 12 Months following First Dose of Study Medication (+/- 4 weeks)

All procedures performed in Visit 5 will be repeated.

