14.0 Stopping Rules/Termination of Study Enrollment

The triggering of stopping rules will result in prompt discontinuation of subject enrollment, subject dosing and notification of the Medical Monitor and IRBs. Although dosing and enrollment will cease, all subjects currently taking or have completed Study Medication treatment up until that point will be followed according to the protocol for the occurrence of adverse events. Efficacy follow-up will be continued only if, in the Principal Investigators judgment, efficacy follow-up would be clinically meaningful. Subject dosing and enrollment will be reconvened only when permission is granted by the IRB.

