15.4 General Data Handling, Analysis, and Reporting Strategy

Intent-to-treat analysis will be performed.

Baseline covariates will be summarized and reported in a table, stratified by group. This is a randomized trial, thus the expected population group differences with respect to baseline covariates are zero by definition. For this reason, no statistical comparisons will be performed to test for differences in baseline covariates between groups.

Whenever applicable, assessment of endpoints that are measured at serial time points will be analyzed using methods that account for this repeated measure structure. Listwise deletion in response to missing data points and categorization/dichotomization of continuous measurements will be avoided to every extent possible.

Summary statistics will be reported as group medians with quartiles or extrema. Meanwhile estimates calculated for statistical inference will be reported with $(1-\alpha)\%$ confidence intervals. Model fit and satisfactorily meeting model assumptions will be assessed for all multivariable regression and linear mixed-effects models using residual analysis.

The Statistical Computing Language R will be used to produce all analyses and plots.

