15.5.2.3 Pain and PRO Assessment

The hypothesis in this study is that FIS will induce a systemic anti-inflammatory and senolytic effect, thereby reducing pain and improving self-reported function and quality of life compared to the placebo group. Early subjective assessment (every 3 days for 6 weeks following the first dose of study medication and once weekly for the following 6 weeks) will be limited to a short augmented numerical rating scale questionnaire. Linear mixed-effect random-intercepts modeling will be used to characterize the trend in self-reported pain over 3 months, and to test whether treatment group is a significant predictor of pain reduction.

The IKDC, WOMAC, Tegner activity scale and Lysholm PRO measures will be administered at 2 weeks after the last dose of study medication and 6, 12, and 18 months following initiation of medication. For each time point, ANCOVA will be used with the subject's baseline PROM value used as a covariate. Among the 4 postoperative time-points for assessing these validated PROMs, the Holm-Bonferroni method will be used to control the family-wise type-1 error rate to 0.05 within each PROM scale tested. No multiplicity adjustments will be made across different PROMs, which are commonly highly intercorrelated.

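### Visit 4 is timed from each subject's own last dose, so a subject who stops after the first course is due about 30 days early, or has no attainable visit window, and the Visit 4 PRO analysis can mix two times sorted by adherence

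*Combined protocol and SAP*

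**What the plan says.** The Visit 4 heading in section 10.3 reads "Visit 4: Two Weeks from the Subject's Last Dose of Fisetin or Placebo (+/- 10 days"), and the text below it applies this to everyone: "All subjects will return to the study site two-weeks from the subject's last dose of Fisetin (FIS) or placebo". The Synopsis, section 6.0 and Appendix B use the same last-dose anchor. At this visit the plan collects questionnaires, blood, vital signs, a physical exam and adverse events.

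The dosing calendar in 10.1 is: "Subjects will be instructed to self-medicate for day 2 followed by 28 days off". Then: "A second course will be taken for two consecutive days (days 31 and 32").

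The analysis plan, 15.5.2.3, has the IKDC, WOMAC, Tegner and Lysholm "administered at 2 weeks after the last dose of study medication and 6, 12, and 18 months following initiation of medication". Each time point gets its own ANCOVA with the baseline score as covariate. Holm-Bonferroni is applied over the four times within each scale. Section 15.4 adds: "Intent-to-treat analysis will be performed".

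No section gives a nominal study day for Visit 4, says what happens to a subject who does not take the second course, or assigns assessments to time points by actual day. Section 11.5 uses another anchor again: it counts remote questionnaires at 3 and 18 months from completion of medication.

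**The concern.** A time point anchored to the last dose actually taken moves with adherence, and adherence is observed after randomisation. Section 13.1 lists nausea, vomiting and diarrhea among the possible side effects of fisetin, so stopping after the first course could differ between arms. An intent-to-treat ANCOVA labelled Visit 4 would then compare groups that differ in when they were measured as well as in treatment. Some values would describe one course at two weeks, and the rest two courses at six to seven weeks.

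There is also a follow-up gap. A subject seen on day 16 has used up Visit 4. The next scheduled labs, exam and visit-based adverse event review are at Visit 5, six months +/- 4 weeks after first dose.

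**Working it through.** **Inputs.** Day 1 is the first dose (6.0). The first course is days 1 and 2, then 28 days off, then days 31 and 32 (10.1). Visit 3 is "Two Weeks after first dose of Fisetin or Placebo (+/- 2 days"), from the 10.2 heading and Appendix B. (The sentence under that heading says last dose; that also needs reconciling.) Visit 4 is last dose + 14 days, +/- 10 days (10.3).

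**The plan's own figure.** 2 + 28 + 1 = day 31, then day 32. This agrees with the stated second course.

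**Visit 4 due day = last dose + 14; window = due day +/- 10.**

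| Doses taken | Last dose | Visit 4 due | Window |
|---|---|---|---|
| Both courses | 32 | 46 | 36 to 56 |
| First course and day 31 | 31 | 45 | 35 to 55 |
| First course only | 2 | 16 | 6 to 26 |
| Day 1 only | 1 | 15 | 5 to 25 |

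Visit 3 is due on day 1 + 14 = 15, window 13 to 17.

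The both-course and first-course-only due days differ by 46 - 16 = 30 days. The early window ends on day 26 and the later one starts on day 36, so they are 10 days apart and do not overlap. The early window contains the whole Visit 3 window.

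**Who can be seen on day 16.** Only a subject whose stop is known by day 26. The Synopsis puts a reminder call 2 to 4 days before the last dosing, which is days 27 to 29 counting back from day 31. A subject who declines at that call, or skips days 31 and 32, is already outside 6 to 26. The visit then cannot be held as written, and its day is undefined.

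**Effect on mean assessment day.** The documents give no rate for stopping after the first course. If a share p stops and is seen on day 16, the mean Visit 4 day is 46 - 30p: 44.5 at 5%, 43.0 at 10%, 40.0 at 20%. With 36 per arm (6.0), those shares are 1.8, 3.6 and 7.2 subjects.

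**Illustrative bias.** Assume 15% stop on fisetin and 5% on placebo, all known by day 26, and scores drift by 0.3 to 0.5 SD between day 16 and day 46, equally in both arms. None of these figures is in the documents.

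- Bias = (0.15 - 0.05) x drift = 0.10 x 0.3 to 0.10 x 0.5 = 0.03 to 0.05 SD.
- Unadjusted standard error of a standardised difference = sqrt(2/n): sqrt(2/36) = 0.24 and sqrt(2/50) = 0.20, for 36 per arm or the 50 per arm implied by the maximum of 100.
- Ratio: 0.03/0.24 = 0.13 to 0.05/0.20 = 0.25 of one standard error. Baseline adjustment would shrink the standard error and raise this ratio somewhat.

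**The case against.** **Last dose may mean the planned one.** The Synopsis uses last dosing for the scheduled second course, and on that reading everyone is due about day 46. The possessive in 10.3 points the other way. Two readings 30 days apart need one clarifying sentence.

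**Anchoring a safety visit to last exposure is legitimate.** It is, and for that reason subjects who take the second course should keep the present timing. The argument does not carry over to a questionnaire time point compared between arms.

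**Non-compliant subjects may be removed.** Section 14.3 permits this at discretion. Relying on it would sit badly with intent-to-treat.

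**The effect is small.** This stands. It touches one of four times for secondary endpoints. The NRS series, and the 6-, 12- and 18-month analysis times as 15.5.2.3 states them, run from the first dose.

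Four stronger readings are tempting and are not supported:

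- A reader might infer a 30-day shift for every subject who misses the second course. It applies only if the stop is known by day 26; for the others the visit day is undefined.
- A reader might take section 14.0 to send all subjects halted between courses into the Visit 4 ANCOVA: "Although dosing and enrollment will cease, all subjects currently taking or have completed Study Medication treatment up until that point will be followed". The same sentence limits that follow-up to adverse events, and efficacy follow-up then depends on the investigator's judgment. A halt also affects both arms, so it does not make timing depend on tolerance.
- A reader might infer that Visit 4 is the only time point not counted from first dose. Section 11.5 counts its remote questionnaires from completion of medication.
- A reader might infer a biased adverse event comparison. Section 12.2 records events since the previous visit or whenever reported, and 15.5.1 analyses them by subject or count and not by visit.

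**Conclusion.** The point holds in a limited form. As written, Visit 4 has two non-overlapping due times that depend on adherence, and none that can be met for a subject whose stop is learned after day 26. The intent-to-treat Visit 4 questionnaire ANCOVA has no term for actual day and no rule to separate the two times. Subjects who stop early also have no scheduled labs, exam or visit-based adverse event review between about day 16 and Visit 5, although a remaining phone call, unscheduled contact and spontaneous reports can still capture events.

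The number affected is unknown. The bias is probably small: 0.03 to 0.05 SD under the assumed 15% against 5% stopping and 0.3 to 0.5 SD drift. No visit-specific model is given for the blood markers, so no effect on them can be derived. The reason to act is an undefined time point that is cheap to define, not a large expected bias.

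**What to change.** State that a subject who does not take the second course, for any reason, has Visit 4 at the nominal time counted from first dose: day 46 +/- 10 days, which is 14 days after scheduled day 32. Subjects who take the second course keep the present timing. This changes assessment timing only, not dosing. The window stays open to day 56, so it can still be met when a missed course is discovered on day 31 or 32.

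Make the same change in the Synopsis, 6.0, 10.3, 15.5.2.3 and Appendix B, and reconcile the anchor in 11.5 with them. In the analysis plan, use the Visit 4 label only for assessments at that nominal time by days since first dose, with a documented allowance for a delayed second course.

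A fixed day 46 for everyone would be simpler but worse. The documents give no window for the second course, and one finishing after day 42 could not be followed by a visit 14 days later within day 56 (42 + 14 = 56).

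The cost is protocol and SAP wording, one later visit for early stoppers, and slightly variable timing when the second course is delayed. Subjects dosed on schedule see no change.

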10.6 Additional Remote Follow-up

In addition to the in-clinic follow-up visits above, the following remote follow-up will be conducted:

10.6.1 Once Every 3 days During FIRST 6 weeks of Study Medication then Once a Week for an ADDITIONAL 6 weeks

Subjects will complete an augmented NRS questionnaire.

10.6.2 18-Months After First Dose of Study Medication (+/- 4 weeks)

Subjects will complete the augmented PROs electronically, including: NRS, IKDC, Lysholm, TEGNER, WOMAC and SF-12 questionnaires.

10.7 Unscheduled Visits and/or Subject Contact

In the event that additional visit(s) or subject contact is made other than those described in the protocol, all data must be documented in the appropriate study document including the occurrence or adverse events and/or protocol deviations.

10.8 Phone Calls

Subjects will be contacted by phone three times while they are taking study medication to remind them to take the next dose of drug and to capture any adverse events.

11.0 Study Tools

11.1 Vital Signs (Visits 1, 3, 4, 5, 6)

Vital signs are to include measurement of temperature, blood pressure and heart rate.

11.2 Physical Exam: (Visits 1, 4, 5, 6)

Physical exams are to include height, weight, ROM of the target limb, and general wellness check up to examine any adverse events.

11.3 Range of Motion (ROM): (Visits 1, 4, 5, 6)

Both the active and passive range of motion should be assessed. The normal knee extension is between 0 to 10 degrees. The normal knee flexion is between 130 to 150 degrees. Any pain, abnormal movement, or crepitus of the patella will be noted.

11.4 Blood Laboratory Analysis: (Visits 1, 3, 4, 5, 6)

Analyses in Column A will be performed by a CLIA-Certified Laboratory:
Vail Health Laboratory.

Analyses in Column B will be performed at the Steadman-Philippon Research Institute (SPRI)

Column A	Column B
CBC w/Diff	
T-Cell Assay: Peripheral blood CD3+ T cell assay for P16INK4a: 30 mL blood will be collected using EDTA tubes to measure p16 INK positive lymphocyte population in the peripheral blood- a biomarker of senescence and chronological aging. T-Cells will be enriched from whole blood using a commercial kit following manufactures instructions (RosetteSep, Stem Cell Technologies #15021). P16 expression will be measured by RT-PCR using Taq-man primer-probe system from enriched T-cells.
 
C₁₂FDG Detection of Senescent Cells in Flow: A portion of enriched T-cells collected from 30 ml blood described above will be stained with C₁₂FDG, a fluorescent marker to detect senescent cells using flow cytometry (Guava EasyCyte, Luminex).
 
Biomarker Assessment for Senescent cells: Quantification of Growth Factor and Cytokine/Chemokine Composition: The whole blood sample will be pipetted to microcentrifuge tubes for Luminex® multiplex immunoassays (EMD Millipore Corp, Billerica, MA) that measure concentrations of growth factors, cytokines and chemokines. Specific immunoassay kits (EMD Millipore Corp, Billerica, MA) a human cytokine/chemokine magnetic bead panel, TGF-β magnetic bead panel, MMP magnetic

CMP	
CRP	
ESR	
Creatine Kinase	
Uric Acid	
Vit D (25 hydroxy)	
Hb A1c	

bead panel 1, and MMP magnetic bead panel 2. A standard manufacturer's protocol for the Luminex® 200 (Luminex Corp, Austin, TX) multiplex instrument will be utilized as previously published (64). Plate will be analyzed with the Luminex® 200 xPONENT 3.1 system (Luminex Corp, Austin, TX) using the xPonent® software (EMD Millipore Corp, Billerica, MA), which created a standard curve for each respective analyte utilizing a five-parameter logistic curve-fitting method with the median fluorescent intensity. The proteins to be assayed include: sCD40L, EGF, Eotaxin, FGF-2, Flt-3, IFN- α 2, IFN- γ , IL-1 α , IL-1 β , IL-1ra, IL-2, IL-3, IL-4, IL-5, IL-6, IL-7, IL-8, IL-9, IL-10, IL-12 (p40 and p70), IL-13, IL-15, IL-17A, IP-10, MCP-1, MCP-3, MDC, MIP-1 α , MIP-1 β , PDGF-AA, PDGF-AB/BB, RANTES, TGF- α , TNF- α , TNF- β , VEGF, MMP (1,2,3,7,9,10,12,13), TGF- β (isoforms 1,2,3).

11.5 Patient Reported Outcomes (PROs): (Visits 1, 2, 4, 5, 6)

All PROs may be completed either on paper documents or by online questionnaire administration conducted via formsite (Vroman Systems, Inc.). Patients may complete questionnaires on a variety of electronic devices (personal computer, mobile phone, tablet).

PRO data to be collected include:

Augmented Numerical Rating Scale (NRS) (visit 2): At baseline then once every 3 days during FIRST 6 weeks of study medication treatment then once a week for an ADDITIONAL 6 weeks.

IKDC, Lysholm, TEGNER, WOMAC and SF-12 (visit 2, visits 4, 5, and 6 and remote assessments at 3- and 18-months post completion of medication).

The Numerical Rating Scale is a simple 0-10 self-reported severity of pain scale, (zero being no pain and 10 being the worst pain imaginable). This tool has been validated to provide excellent test-retest reliability in assessing knee pain associated with OA³¹. The Steadman Philippon Research Institute has added several stand-alone questions that are administered with the questionnaire. Only the validated portion, the simple NRS will be used to screen patients. In follow-up, each question will be analyzed individually. There is no composite score. A sample can be found in **Appendix C, Section 22.3** of this document.

The Lysholm knee scale is a condition-specific outcome measure that was originally designed to assess ligament injuries of the knee. It has been tested to provide excellent construct validity and overall acceptable psychometric performance for outcomes assessment of various chondral disorders of the knee. It is recommended that this tool be administered with additional psychometric measurements^{32,33}.

The TEGNER Activity Scale is a numerical scale ranging from 0 to 10. Each value indicates the ability to perform specific activities. An activity level of 10 corresponds to participation in the most physically demanding activities while a zero is assigned if a person is on sick leave or receiving a disability pension because of knee problems. It is simple to use, and it has been demonstrated to provide acceptable psychometric performances as outcome measures for patients with a meniscal injury of the knee. Like the Lysholm, it is recommended that it be used in conjunction with other psychometric tools such as the SF 12³².

The Western Ontario and MacMaster Universities (WOMAC) Osteoarthritis Index is a widely used self-administered health status measure assessing pain, stiffness, and function in patients with OA of the hip or knee. It has been demonstrated to fulfill conventional criteria for face, content and construct validity, reliability, responsiveness and relative efficiency. It has been shown to be an excellent instrument for evaluative research in osteoarthritis clinical trials³⁴.

The SF-12 is a short form of the SF-36 which is a widely accepted tool, known to provide a validated method to assess quality of life in physical and mental domains³⁵.

The SF-12 has been validated against the SF-36 and has been shown to demonstrate the empirical validity of the 12-item short-form (SF-12) health survey summary measures and 8-scale profile in comparison with SF-36 summary measures and scales³⁶.

11.6 Imaging Assessment of OA

11.6.1 Radiographic Assessment: (Visit 1)

Subjects will receive baseline radiographs of the knee(s). If a subject has had a satisfactory radiograph within the previous 6 months of screening, no additional radiograph is required.

The knee joint is typically evaluated using the extended-knee radiograph, which is a bilateral anteroposterior image acquired while the patient is weight-bearing, with both knees in full extension. More recently, flexed-knee radiographs with varying degrees of flexion and x-ray beam angles have been employed to improve intra-articular visualization. Radiographs are used to evaluate osteophyte formation and joint space narrowing (JSN); grading schemes such as the Kellgren-Lawrence grading scheme³⁷ and the Osteoarthritis Research Society International classification score establish guidelines for the diagnosis of OA progression³⁷.

11.6.2 Quantitative Magnetic Resonance Imaging (MRI): (Visits 2, 5, 6)

Quantitative MRI will be performed at the Steadman clinic. In preparation for MRI, subjects will be asked to remove their shoes and any metal that may interfere with the scan (e.g. metallic clothing, jewelry) and will be provided with disposable, MRI-compatible clothing if needed.

Images will be acquired on a 3T Siemens Magnetom Skyra-fit scanner.

For the screening and follow-up MR scans, morphological T1 MR images will be acquired. These images provide evaluation of knee structure. It is well known that structural alteration can lead to loss of collagen organization (e.g., torn fibers and scar tissue) and changes in water content (e.g., dehydration).

In addition, quantitative T2 MR images, which provide data on tissue MR signal relaxometry values, will be acquired to provide information regarding cartilage health including the relative level of water and collagen organization within the tissue.

A Study Team member will physically collect the hard drive and will transfer MR images to the SPRI Imaging Research network drive, accessible only to specific SPRI personnel via password protected accounts. The images will also be uploaded to the secure TSC PACS (Picture Archiving And Communication System) for radiological assessment by a blinded radiologist. Objective morphological measurements and Quantitative MRI value analysis will be performed from the DICOM files using Mimics, ImageJ, 3D Slicer, and MATLAB. Specifically, the regions of interest will be segmented in either Mimics or 3D Slicer (equivalent function software) and the masks will be exported to BPM format (bitmap) and imported into MATLAB for extraction of T2 or T2 values within the regions of interest. Morphological measurements may be taken in either Mimics, ImageJ, or 3D Slicer depending upon software scheduling coordination. All of these programs perform equivalently for this purpose. Results will be output to an Excel spreadsheet for statistical analysis.

